### 7.1. Screening and Baseline Assessments

A signed, written informed consent form must be obtained from the subject's guardian prior to any screening or study-specific procedures or assessments. Subjects over 6 years old will be asked to sign an assent form.

Subjects must be screened to ensure they meet the eligibility criteria specified in Section 4.1, Subject Selection Criteria. Screening assessments will be performed within 4 weeks (28 days) prior to the first dose of study treatment. All screening and baseline evaluations must be completed prior to initiating study treatment. The following baseline results must be reviewed prior to initiating study treatment, including:

• Urine or serum pregnancy test, for females of childbearing potential, within 24 hours of first dose of study treatment.

The required screening assessments are outlined in Table 3, Time and Events Table.

If a subject is not eligible for the study per the Inclusion and Exclusion Criteria at the initial attempt, and in the investigator's opinion the subject may become eligible at a later date during the enrolment period, the investigator is allowed to re-screen the subject.

## 7.2. Safety

## 7.2.1. Safety Endpoints

Safety and tolerability endpoints include clinical laboratory assessments and frequency of all adverse events, categorized using Common Terminology Criteria for Adverse Events (CTCAE) toxicity grades. Refer to the SPM for current version.

#### 7.2.1.1. General Considerations

Once the dose of eltrombopag and other ITP medications has been stable for 3 consecutive weeks, which may include the prior 3 weeks in the TRA115450 study, monthly visits will be acceptable unless in the investigator's opinion there is a specific medical reason for more frequent evaluations. If the dose is not stable, weekly visits will be required.

Planned time points and more detailed information for all safety assessments are listed in the Time and Events Tables (Section 7 Table 3).

### 7.2.1.2. Physical Exam and Vital Signs

#### Physical Exam

A physical examination will be done at Day 1 per the investigator's usual practice and any abnormal findings will be recorded on the appropriate form in the CRF, e.g, Medical History or AE/SAE form.

#### 7.2.1.3. Clinical Laboratory Assessments

Hematology and clinical chemistry parameters to be tested are listed in Section 7.2.4; Table 4 lists the parameters to be tested locally. The amount of blood drawn for all routine clinical laboratory assessments for this study is anticipated to be approximately 15-20 mL per study visit. Every effort will be done to reduce this to a minimum according to each local lab's requirements.

#### 7.2.1.4. Cataract Assessment

Ophthalmic safety, with focus on cataracts, will be assessed in all subjects following procedures used in standard practice at the times listed in the Time and Events Table.

Ocular examinations will be performed by an ophthalmologist or an optometrist under the guidance of an ophthalmologist. Assessments should be performed, whenever possible, by the same examiner.

Any abnormal findings will be recorded in the appropriate CRF form, e.g., Medical History or AE/SAE form.

#### 7.2.1.4.1. Ocular Changes of Clinical Concern

Ophthalmic events of clinical concern as defined by the examiner, include, but are not limited to:

- Decreased vision due to cataractous changes;
- Progressive lens changes: Worsening cataractous changes observed on slit lamp examination; and
- Need for cataract surgery.

#### 7.2.2. Adverse Events

The investigator or site staff will be responsible for detecting, documenting and reporting events that meet the definition of an AE or SAE as outlined in Section 7.2.2.1 and Section 7.2.2.2.

#### 7.2.2.1. Definition of an AE

An AE is any untoward medical occurrence in a subject or clinical investigation subject, temporally associated with the use of a medicinal product, whether or not considered related to the medicinal product.

Note: An AE can therefore be any unfavorable and unintended sign (including an abnormal laboratory finding), symptom, or disease (new or exacerbated) temporally associated with the use of a medicinal product. For marketed medicinal products, this also includes failure to produce expected benefits, abuse, or misuse.

Examples of events meeting the definition of an AE include:

- Exacerbation of a chronic or intermittent pre-existing condition including either an increase in frequency and/or grade of the condition
- New conditions detected or diagnosed after study treatment administration even though it may have been present prior to the start of the study
- Signs, symptoms, or the clinical sequelae of a suspected interaction
- Signs, symptoms, or the clinical sequelae of a suspected overdose of either study treatment or a concomitant medication (overdose per se will not be reported as an AE/SAE unless this is an intentional overdose taken with possible suicidal/self-harming intent. This should be reported regardless of sequelae).
- "Lack of efficacy" or "failure of expected pharmacological action" *per se* is not to be reported as an AE or SAE. However, any signs and symptoms and/or clinical sequelae resulting from "lack of efficacy" will be reported as an AE or SAE, if they fulfill the definition of an AE or SAE.

Events that **do not** meet the definition of an AE include:

- Medical or surgical procedure (e.g., endoscopy, appendectomy); the condition that leads to the procedure is an AE.
- Situations where an untoward medical occurrence did not occur (social and/or convenience admission to a hospital).
- Anticipated day-to-day fluctuations of pre-existing disease(s) or condition(s) present or detected at the start of the study that do not worsen.
- The disease/disorder being studied, or expected progression, signs, or symptoms of the disease/disorder being studied, unless more severe than expected for the subject's condition.

#### 7.2.2.2. Definition of a SAE

A serious adverse event is any untoward medical occurrence that, at any dose:

- a. Results in death
- b. Is life-threatening
  - NOTE: The term 'life-threatening' in the definition of 'serious' refers to an event in which the subject was at risk of death at the time of the event. It does not refer to an event, which hypothetically might have caused death, if it were more severe.
- c. Requires hospitalization or prolongation of existing hospitalization
  - NOTE: In general, hospitalization signifies that the subject has been detained (usually involving at least an overnight stay) at the hospital or emergency ward for observation and/or treatment that would not have been appropriate in the physician's office or out-subject setting. Complications that occur during hospitalization are AEs. If a complication prolongs hospitalization or fulfils any other serious criteria,

the event is serious. When in doubt as to whether "hospitalization" occurred or was necessary, the AE should be considered serious.

Hospitalization for elective treatment of a pre-existing condition that did not worsen from baseline is not considered an SAE.

#### d. Results in disability/incapacity, or

NOTE: The term disability means a substantial disruption of a person's ability to conduct normal life functions. This definition is not intended to include experiences of relatively minor medical significance such as uncomplicated headache, nausea, vomiting, diarrhea, influenza, and accidental trauma (e.g. sprained ankle) which may interfere or prevent everyday life functions but do not constitute a substantial disruption.

- e. Is a congenital anomaly/birth defect.
- f. Medical or scientific judgement should be exercised in deciding whether reporting is appropriate in other situations, such as important medical events that may not be immediately life-threatening or result in death or hospitalization but may jeopardize the subject or may require medical or surgical intervention to prevent one of the other outcomes listed in the above definition. These should also be considered serious. Examples of such events are invasive or malignant cancers, intensive treatment in an emergency room or at home for allergic bronchospasm, blood dyscrasias or convulsions that do not result in hospitalization, or development of drug dependency or drug abuse.

# g. Protocol-Specific SAEs

• All events of possible drug-induced liver injury with hyperbilirubinaemia defined as ALT ≥ 3xULN and bilirubin ≥ 2xULN (>35% direct) (or ALT ≥ 3xULN and INR>1.5, if INR measured) or termed 'Hy's Law' events (INR measurement is not required and the threshold value stated will not apply to patients receiving anticoagulants).

NOTE: bilirubin fractionation is performed if testing is available. If testing is unavailable, record presence of detectable urinary bilirubin on dipstick indicating direct bilirubin elevations and suggesting liver injury. If testing is unavailable and a subject meets the criterion of total bilirubin  $\geq 2xULN$ , then the event is still reported as an SAE. If INR is obtained, include values on the SAE form. INR elevations >1.5 suggest severe liver injury

- All Grade 4 laboratory abnormalities assessed using the National Cancer Institute (NCI) Common Terminology Criteria for Adverse Events (CTCAE) (see The Study Procedures Manual for: Common Terminology Criteria for Adverse Events), except Grade 4 thrombocytopenia.
- An ocular event of clinical concern as defined in Section 7.2.1.4.1 Ocular Changes of Clinical Concern.

# 7.2.2.3. Laboratory and Other Safety Assessment Abnormalities Reported as AEs and SAEs

Any abnormal laboratory test results (hematology, clinical chemistry, or urinalysis), or other safety assessments (e.g., ECGs, radiological scans, vital signs measurements) including those that worsen from baseline, and events felt to be clinically significant in the medical and scientific judgment of the investigator are to be recorded as an AE or SAE, in accordance with the definitions provided.

In addition, an associated AE or SAE is to be recorded for any laboratory test result or other safety assessment that led to an intervention, including permanent discontinuation of study treatment, dose reduction, and/or dose interruption/delay.

However, any clinically significant safety assessments that are associated with the underlying disease, unless judged by the investigator to be more severe than expected for the subject's condition, are not to be reported as AEs or SAEs.

Bleeding events should be reported as an AE or SAE as appropriate according to the Investigator's judgment.

# 7.2.2.4. Disease-Related Events and/or Disease-Related Outcomes Not Qualifying as SAEs

Thrombocytopenia that results in the administration of rescue medication is to be considered treatment failure rather than an AE or SAE.

#### 7.2.2.5. Time Period and Frequency of Detecting AEs and SAEs

The investigator or site staff is responsible for detecting, documenting and reporting events that meet the definition of an AE or SAE.

AEs will be collected from the time the first dose of study treatment is administered until the 4-week follow-up visit.

SAEs will be collected over the same time period as stated above for AEs. In addition, any SAE assessed **as related** to study participation (e.g., protocol-mandated procedures, invasive tests, or change in existing therapy) or study treatment must be recorded from the time a subject consents to participate in the study up to and including the 4-week follow-up period. All SAEs will be reported to GSK within 24 hours, as indicated in Section 7.2.2.6.

After discontinuation of study treatment, the investigator will monitor all AEs/SAEs that are ongoing until resolution or stabilization of the event or until the subject is lost to follow-up. At any time after the 4-week follow-up visit the investigator may report any adverse event that they believe possibly related to study treatment.

#### 7.2.2.6. Prompt Reporting of SAEs and Other Events to GSK

SAEs, pregnancies, and liver function abnormalities meeting pre-defined criteria will be reported promptly by the investigator to GSK as described in the following table once the investigator determines the event meets the protocol definition for that event.

	Initial Reports	Reports Follow-up Information on a Previous Report		
Type of Event	Time Frame	Documents	Time Frame	Documents
All SAEs	24 hours	SAE data collection tool	24 hours	Updated SAE data collection tool
Pregnancy	2 Weeks	Pregnancy Notification Form	2 Weeks	Pregnancy Follow up Form
Liver chemistry abnorn	nalities:			
ALT≥3xULN and bilirubin≥1.5xULN (>35% direct) (or ALT≥3xULN and INR>1.5, if INR measured)³	24 hours 	SAE data collection tool. Liver Event Case Report Form (CRF) and liver imaging and/or biopsy CRFs if applicable 	24 hours	Updated SAE data collection tool. Updated Liver Event CRF 
ALT≥5xULN; ALT≥3xULN with hepatitis or rash or ALT ≥3xULN and <5xULN that persists ≥4 weeks	24 hours 	Liver Event CRF 	24 hours	Updated Liver Event CRF 
ALT≥3xULN and <5xULN and biliribin <1.5xULN	24 hours 	Liver Event CRF does not need completing unless elevations persist for 4 weeks or subject cannot be monitored weekly for 4 weeks 		

- 1. GSK to be notified at onset of liver chemistry elevations to discuss subject safety.
- 2. Liver event documents should be completed as soon as possible
- 3. INR measurement is not required; if measured, the threshold value stated will not apply to subjects receiving anticoagulants.

Methods for detecting, recording, evaluating, and following up on AEs and SAEs plus procedures for completing and transmitting SAE reports to GSK are provided in the SPM. Procedures for post-study AEs/SAEs are provided in the SPM.

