#### Liver chemistry stopping criteria 1-5 are defined as follows:

1. ALT  $\ge 3x$  ULN and bilirubin  $\ge 2x$  ULN (>35% direct bilirubin) (or ALT  $\ge 3x$  ULN and INR > 1.5, if INR measured)

**NOTE:** If serum bilirubin fractionation is not immediately available, study drug should be discontinued if  $ALT \ge 3x$  ULN **and** bilirubin  $\ge 2x$  ULN. Serum bilirubin fractionation should be performed if testing is available. If testing is unavailable, **record presence of detectable urinary bilirubin on dipstick**, indicating direct bilirubin elevations and suggesting liver injury.

- 2. ALT > 5x ULN
- 3. ALT  $\geq$  3x ULN if associated with symptoms (new or worsening) believed to be related to hepatitis (such as fatigue, nausea, vomiting, right upper quadrant pain or tenderness, or jaundice) or believed to be related to hypersensitivity (such as fever, rash or eosinophilia).
- 4. ALT > 3x ULN persists for > 4 weeks
- 5. ALT  $\geq$  3x ULN and cannot be monitored weekly for 4 weeks

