### When any of the liver chemistry stopping criteria 1 - 5 is met, do the following:

- Immediately discontinue study treatment
- Report the event to GSK within 24 hours of learning its occurrence
- Complete the liver event CRF and SAE data collection tool if the event also meets the criteria for an SAE
  - All events of ALT ≥ 3x ULN and bilirubin ≥ 2x ULN (>35% direct bilirubin) (or ALT ≥3x ULN and INR > 1.5, if INR measured; INR measurement is not required and the threshold value stated will not apply to subjects receiving anticoagulants), termed 'Hy's Law', must be reported as an SAE (excluding studies of hepatic impairment or cirrhosis).
  - NOTE: if serum bilirubin fractionation is not immediately available, study treatment should be discontinued if ALT ≥ 3x ULN and bilirubin ≥ 2x ULN. Serum bilirubin fractionation should be performed if testing is available. If testing is unavailable, record presence of detectable urinary bilirubin on dipstick, indicating direct bilirubin elevations and suggesting liver injury.
- Complete the liver imaging and/or liver biopsy CRFs if these tests are performed
- Perform liver event follow up assessments, and monitor the subject until liver chemistries resolve, stabilize, or return to baseline values as described below
- Do not rechallenge with investigational product.

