## 5.8.1.2. Liver Chemistry Monitoring Criteria

For subjects with ALT  $\ge 3x$  ULN **but** < 5x ULN **and** bilirubin < 2x ULN, without hepatitis symptoms or rash, and who can be monitored weekly for 4 weeks, the following actions should be taken:

- Notify the GSK Medical Monitor within 24 hours of learning of the abnormality to discuss subject safety
- Can continue study treatment
- Must return weekly for repeat liver chemistries (ALT, AST, alkaline phosphatase, bilirubin) until they resolve, stabilize or return to within baseline values
- If at any time the subject meets any of the liver chemistry stopping criteria 1-5, proceed as described above
- If, after 4 weeks of monitoring, ALT <3x ULN and bilirubin <2x ULN, monitor subjects twice monthly until liver chemistries normalize or return to within baseline values.

Refer to Appendix 1 for algorithm of liver chemistry monitoring, stopping and follow up criteria.

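### The prompt-reporting table calls for the SAE form from bilirubin 1.5xULN, while the SAE definition and the liver rules use 2xULN, and one ALT/bilirubin band fits no liver row at onset

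*Protocol*

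**What the plan says.** The table in Protocol 7.2.2.6 has three liver rows.

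- **Row 1** starts at "ALT≥3xULN and bilirubin≥1.5xULN (>35% direct", with an INR alternative. It asks for the SAE data collection tool and the Liver Event CRF.
- **Row 2** covers ALT of 5xULN or more, ALT of 3xULN or more with hepatitis or rash, and ALT from 3 to below 5xULN lasting at least 4 weeks. It asks for the Liver Event CRF only.
- **Row 3** is "ALT≥3xULN and <5xULN and biliribin <1.5xULN". It asks for notification, normally without the Liver Event CRF.

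The table's lead-in says that reporting applies "once the investigator determines the event meets the protocol definition for that event".

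The other current sections use a different bilirubin cut-off. Protocol 7.2.2.2 (g) has a protocol-specific SAE "defined as ALT ≥ 3xULN and bilirubin ≥ 2xULN (>35% direct". If fractionation is unavailable and total bilirubin is at least 2xULN, "then the event is still reported as an SAE". The actions listed in 5.8.1 make SAE reporting mandatory for "All events of ALT ≥ 3x ULN and bilirubin ≥ 2x ULN (>35% direct bilirubin", and otherwise ask for the SAE tool only when the event meets SAE criteria. Stopping criterion 1 uses 2xULN, as does its note beginning "If serum bilirubin fractionation is not immediately available, study drug should be discontinued if". Section 5.8.1.2 lets treatment continue under weekly monitoring when ALT is from 3 to below 5xULN with "bilirubin < 2x ULN, without hepatitis symptoms or rash, and who can be monitored weekly for 4 weeks".

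**The concern.** The same laboratory result is handled differently depending on which section a site opens. Under the table it goes on an SAE form. Under the definition it is not a protocol-specific SAE, and under 5.8.1.2 it can be an ordinary monitoring case. The table also leaves some results without a row.

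This is a descriptive safety study of at most 12 children, so a single event is visible in every table. If sites treat the form as settling seriousness, an event moves between the SAE and non-SAE tables of SAP 2.6.1. Uneven completion of the Liver Event CRF would likewise affect the liver-event listings in SAP 2.6.3 and 2.6.4.1.

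**Working it through.** **Step 1. Cut-offs side by side (current protocol text).**

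| Section | What it decides | Bilirubin | Direct fraction |
|---|---|---|---|
| 5.8.1, criterion 1 | Stop treatment | ≥2xULN | >35%, or not immediately available |
| 5.8.1, actions | Mandatory SAE report | ≥2xULN | >35% |
| 5.8.1.2 | Continue and monitor | <2xULN | Not used |
| 7.2.2.2 (g) | Protocol-specific SAE | ≥2xULN | >35%, or testing unavailable |
| 7.2.2.6, row 1 | SAE form and Liver Event CRF | ≥1.5xULN | >35% |
| 7.2.2.6, row 3 | Notification | <1.5xULN | Not used |

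The figure 1.5 appears twice in the table, as complementary bounds, so a text-extraction fault is unlikely. Table 3 (note 8) and Table 4 list direct bilirubin as a routine test, so the 35% condition can be assessed below 2xULN.

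**Step 2. Classify results with ALT from 3 to below 5xULN.** Assumptions: onset, no hepatitis symptoms or rash, INR not measured, direct fraction known, weekly monitoring possible.

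| Bilirubin (xULN) | Direct | 7.2.2.6 liver row | Protocol-specific SAE | 5.8.1.2 group |
|---|---|---|---|---|
| <1.5 | Any | Row 3 | No | Yes |
| 1.5 to <2 | >35% | Row 1, SAE form | No | Yes |
| 1.5 to <2 | ≤35% | None | No | Yes |
| ≥2 | >35% | Row 1, SAE form | Yes | No (criterion 1 met) |
| ≥2 | ≤35% | None | No | No |

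Grid check with ALT 3, 4 and 4.9:

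- Bilirubin 1.5, 1.75 and 1.99 at 50% direct gives 3 × 3 = 9 combinations. All 9 fall in the SAE-form row, none is a protocol-specific SAE, and all 9 fall in the monitoring group.
- The same 9 combinations at 20% direct fall in no liver row.
- Bilirubin 2.0 and 2.5 at 20% direct gives 3 × 2 = 6 combinations. All 6 fall in no liver row.

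At ALT 6xULN with bilirubin 1.5 to 1.99xULN and 50% direct, row 1 still asks for the SAE form (3 of 3) and none is a protocol-specific SAE. Stopping criterion 2 applies there regardless.

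**Step 3. Why the gap exists.** Row 1 requires more than 35% direct. Row 2 requires higher ALT, symptoms or 4 weeks' persistence. Row 3 stops at 1.5xULN. The gap is not wholly due to the 1.5 versus 2 mismatch. If both table rows used 2xULN, results with bilirubin at or above 2xULN and at most 35% direct would still have no row.

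**Step 4. Effect of one patient on SAE incidence.** The change is 1/n. The number treated may be below 12, so the range is shown: 1/12 = 8.3, 1/11 = 9.1, 1/10 = 10.0 and 1/8 = 12.5 percentage points.

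**The case against.** The best defence is that the table governs forms and timing, not seriousness. Its lead-in defers to definitions given elsewhere. Section 7.2.2.3 records laboratory abnormalities according to those definitions, and 5.8.1 asks for the SAE tool only when SAE criteria are met. On that reading seriousness on this criterion is fixed at 2xULN throughout, the error runs toward over-reporting, and data cleaning should catch a mislabelled event. That limits the likely harm but does not rescue the wording. If the lead-in governs, row 1's SAE-form requirement has no basis from 1.5 to below 2xULN. If row 1 governs, it contradicts 5.8.1 and 7.2.2.2.

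The gap is also partly covered. For bilirubin from 1.5 to below 2xULN, 5.8.1.2 requires notification within 24 hours whatever the direct fraction, and a table footnote asks for notification when liver elevations begin. Row 2 applies later if the elevation persists or symptoms appear. This stands. It does not reach bilirubin at or above 2xULN with a known direct fraction of at most 35%, where 5.8.1.2 does not apply and only the footnote is left. Leaving mainly indirect elevations out of row 1 may be deliberate, but no text available here says so.

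The SAP liver combination with bilirubin above 2xULN is given only as an example and also involves AST and alkaline phosphatase. It cannot show that the full set of SAP categories is wrong, and the conclusion does not rest on it.

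**Conclusion.** The concern holds. The table conflicts with the four other places on the bilirubin cut-off, and its liver rows do not cover every result at onset.

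The affected band is ALT at least 3xULN, bilirubin from 1.5 to below 2xULN and more than 35% direct. The overlap with continue-and-monitor further needs ALT below 5xULN, no hepatitis symptoms or rash, and feasible weekly monitoring. The uncovered band is ALT from 3 to below 5xULN, bilirubin at or above 1.5xULN and at most 35% direct, with no symptoms and no INR above 1.5.

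The consequence is limited to descriptive SAE tables and liver-event listings, at 8.3 percentage points per patient with 12 treated. The SAP primary endpoint (frequency of all AEs) and the laboratory-based liver summary do not depend on the form used, and the stop and continue rules agree at 2xULN. The documents do not say how often such results occur, so no expected count is given. An event in the band could still be serious for another reason. The Appendix 1 algorithm and the Study Procedures Manual were not available to check and might explain the 1.5xULN figure.

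**What to change.** Reconcile the 7.2.2.6 table with 5.8.1, 5.8.1.2 and 7.2.2.2 (g), so that the SAE definition, the reporting rows and the monitoring rule agree. Assign every bilirubin result to a row, including those at most 35% direct and those not fractionated. Aligning the cut-off alone is not enough, as step 3 shows.

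Alternatively, state in the table that the reporting row is intentionally wider, and that an event with bilirubin from 1.5 to below 2xULN is not a protocol-specific SAE on that ground alone. The uncovered results would still need a row. The threshold is for the sponsor's clinical team to decide.

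Then check that the concurrent ALT and bilirubin categories in SAP 2.6.3 fit the reconciled text. The cost is a table correction or clarifying sentence in an amendment or clarification letter, and a short check of the SAP liver categories.
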